6. ASSIGNMENT AND MASKING

Patients will be selected from a large cohort of known NAION patients who have been attending our facility for at least 12 months (approximately 125 patients). Only patients who meet the inclusion criteria will be selected. Patients will perform a baseline screening visit during which the conditions corresponding to the inclusion criteria will be evaluated and the study proposed. Only after signing the informed consent, will a single investigator ("recruiting doctor"), not involved in the clinical and instrumental assessments, decide whether to assign the selected patient to the Citicoline-treated or non-Citicoline-treated group.

The assignment to either group will take place in sequential order of presentation of the patient (with a 1:1 probability of being assigned to one or the other group) in order to constitute two homogeneous groups in terms of number.

The aforementioned assignment will be known only to the patient and the "recruiting doctor" who will not be involved in the clinical and instrumental assessments envisaged by the research and will therefore be the only investigating doctor to know the group to which the selected patient belongs; this feature of the study will be used to ensure "objectivity" of the clinical and instrumental assessments and to prevent them from being influenced in any way by the knowledge that the patient examined has or has not been treated with Citicoline. In this regard, it should be noted that the patient, by signing the informed consent, promises not to provide any type of information regarding the group to which he/she belongs and/or any treatment administered to other staff of the Institute involved in the clinical and instrumental assessments apart from the "recruiting doctor".

As a result, throughout the duration of the study (both at baseline and at the 6 and 9 month visits),

all study assessments (AV, CV, VEP, PERG, OCT) will be conducted by investigators who do not know if the patient being examined belongs to the Citicoline-treated or non-Citicoline-treated group.

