4. STUDY POPULATION

A number of patients (from a minimum of 16 patients to a maximum of 32) will be enrolled, within a maximum time frame of 24 months, who have a diagnosis of unilateral or bilateral NAION aged 45 to 80 years such as to provide the study 32 eyes affected by this condition with the following

4.1 Inclusion criteria.

- 1) Acute visual reduction episode from NAION occurring for more than 6 months
- 2) Typical defects of the visual field evidenced with the Goldmann perimetry or with Humphrey perimetry 30-2
- 3) Visual acuity not less than 1/10
- 4) Having suspended any potential neuroprotective therapies (e.g., Coenzyme Q10) for at least 6 months.

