5. TRIAL DESIGN

5.1 Trial Plan

A prospective, single-center, randomized, blinded close-label study providing for the enrolment of a minimum of 16 to a maximum of 32 patients (see sample size in the section "Statistics") affected by NAION.

Considering that according to the inclusion/exclusion criteria it is very difficult to recruit patients suffering from NAION with the specific characteristics that enable them to be enrolled in this study, it is likely that with the presence of the binocular NAION, both eyes of the patients will be considered as recruited. Therefore, in the event of all patients having monocular NAION, enrolment must include 32 patients and this number is lower if we need to enrol patients with NAION in both eyes.

Patients selected according to the inclusion/exclusion criteria after signing informed consent will be randomized into two groups:

- a) In one group of patients with NAION no type of treatment will be performed (16 eyes, Control Group)
- b) in another group of patients with NAION, Citicoline will be administered in oral solution (500 mg/day) for 6 months followed by three months of suspension (16 eyes, Treated Group)

The division into two groups will enable the identification of a specific neuroprotective action of Citicoline. Randomization will be done by dividing patients with similar characteristics including age, refraction and visual impairment (perimeter defect and visual acuity) into two groups. Patients will be assigned to each group by an investigator not involved in the functional and structural tests.

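### Sections 5.1 and 6 give unlinked accounts of allocation, and neither says how a sequence is generated, restricted or concealed from the doctor who assigns every patient

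*Combined protocol and SAP*

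**What the plan says.** Two sections of the combined protocol and SAP describe allocation.

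- **Section 5.1 (Trial Plan):** "Randomization will be done by dividing patients with similar characteristics including age, refraction and visual impairment" into two groups. The assigner is an investigator who takes no part in the outcome tests. The same section states what the allocation is for: "The division into two groups will enable the identification of a specific neuroprotective action of Citicoline".
- **Section 6 (Assignment and Masking):** after consent, a single recruiting doctor will "decide whether to assign the selected patient to the Citicoline-treated or non-Citicoline-treated group". Assignment is made "in sequential order of presentation of the patient (with a 1:1 probability of being assigned to one or the other group", and this is done "in order to constitute two homogeneous groups in terms of number".

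On knowledge of the arms, section 6 says: "The aforementioned assignment will be known only to the patient" and the recruiting doctor, who "will therefore be the only investigating doctor to know the group to which the selected patient belongs". All outcome assessments are made by other investigators, who are masked.

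Section 4 plans for a number of patients "from a minimum of 16 patients to a maximum of 32", to supply 32 eyes. Three other places bear on the method without describing it: a randomization entry at baseline in the 5.2 schedule, a key that is opened at the end (5.4), and a randomization number on each CRF page (12.1).

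**The concern.** The claim of a specific treatment effect rests on the two groups being comparable, and 5.1 says so. That depends on the person who assigns being unable to choose or foresee the next arm. Here one doctor assigns every patient and therefore knows all past arms. Candidates come from about 125 patients who have attended the facility for at least 12 months (section 6), so their likely course may already be known to staff.

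A doctor who can choose or anticipate the next arm can influence, even without meaning to, which patients enter which arm or in what order they are put forward. Masked assessors act after allocation and do not prevent this. Adjustment for measured baseline values cannot remove differences in unmeasured prognosis. There is also no placebo to act as a second barrier: the control group is untreated and patients know their arm.

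**Working it through.** The point is mainly textual, so the two sections are first compared item by item.

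- **Who assigns:** 5.1 names an investigator outside the tests; section 6 names the recruiting doctor, also outside the tests. These agree.
- **Rule:** 5.1 divides patients who are similar in age, refraction and visual impairment. Section 6 uses order of arrival with equal probability. Section 6 does not mention the 5.1 characteristics, and 5.1 does not mention order of arrival. They are unlinked.
- **Generation of a sequence:** not stated in either section.
- **Restriction (blocks, strata, minimisation):** not stated. 5.1 hints at matching or stratification, and section 6 states equal numbers as an aim. Neither is an operational rule.
- **Holder of the list, and concealment of the next arm:** not stated. The sentence in section 6 on who knows the assignment names only the patient and the recruiting doctor.

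Order of arrival and a 1:1 probability are compatible with each other: a prepared list used in sequence would satisfy both. The next question is whether a 1:1 probability alone also delivers equal numbers.

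Inputs:
- The target is 16 eyes per group (9.1: 12 × 1.30 = 15.6, rounded up to 16, which reproduces the plan's figure).
- The number of patients is 16 to 32 (section 4). At 32 patients, all with one affected eye, 16/16 eyes means 16/16 patients. At 16 patients, all bilateral, it means 8/8 patients.
- Each patient is assigned independently with probability 1/2.

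The chance of an exact split of N patients is C(N, N/2) / 2^N.
- N = 32: 601,080,390 / 4,294,967,296 = 0.140, or 14.0%.
- N = 16: 12,870 / 65,536 = 0.196, or 19.6%.

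If the aim is only roughly equal numbers, take the chance that the arms differ by 4 or more patients, 2 × Σ C(N, i) / 2^N summed over i = 0 to N/2 − 2.
- N = 32 (14:18 or worse): 59.7%.
- N = 16 (6:10 or worse): 45.4%.

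On either reading, independent 1:1 assignment does not secure the stated aim. Some restriction is implied and none is described.

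Last, the cost in precision if the arms are not exactly equal. Treating eyes as independent, information relative to 16/16 is 4 × n1 × n2 / 32².
- 18/14: 4 × 18 × 14 / 1,024 = 1,008 / 1,024 = 0.984.
- 20/12: 4 × 20 × 12 / 1,024 = 960 / 1,024 = 0.938.

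**The case against.** The strongest reply is that *decide* is being read too hard. The next sentence of section 6 limits it to order of arrival with a 1:1 probability. The study is called randomized, the schedule has a randomization entry at baseline, 5.4 refers to a key, and 12.1 puts a randomization number on each CRF page. A doctor choosing freely would need none of these, and the wording may be loose translation. This stands: a reader might infer that the doctor picks the arm, or that patients simply alternate, and the documents establish neither.

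A reader might also infer that 5.1 and section 6 contradict each other. They do not. Section 5.1 can be read as the aim of comparable groups, and section 6 as order, ratio and masking. The defect is that nothing links them.

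There are partial safeguards. Eligibility is evaluated and consent signed before assignment, the acuity and field criteria are measurable, and the assigner is outside the assessments. These narrow the ways in which selection could occur, but none of them hides the next arm from the person who assigns it.

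**Conclusion.** The point holds as a gap in concealment. As written, the plan permits chosen or foreseeable allocation by a doctor who knows every past arm, in a trial whose main inference rests on randomization. It should be settled before patients are assigned.

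Its limits are these. The front pages and the text between 2.2 and section 4 were not available, so the finding concerns the available text and does not show that no procedure exists. The size of any selection bias cannot be estimated from the documents. The 14.0% and 19.6% figures assume independent assignment by patient. They show that a restriction is missing from the description; they do not measure bias. How predictable the allocation is cannot be quantified either, because the plan names no scheme. The seriousness rests on the missing concealment, with wording that leaves the choice open.

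**What to change.** Replace the allocation text in 5.1 and section 6, including *decide* and *dividing*, with one procedure:

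- A computer-generated 1:1 list with the patient as the unit, so that both eyes of a bilateral patient are in the same arm.
- The list is prepared and held by existing staff who neither recruit nor assess. The Pharmacy is one candidate: it stores the supplement (7.6) and shares its handling with the Investigator (7.5).
- Each assignment is released to the recruiting doctor for one patient at a time, only after consent and baseline tests are recorded. Order of arrival may stay if it means the order in which the list is used.
- State the restriction. Avoid small fixed blocks: a doctor who knows past arms can work out the last assignments in each block.
- Add the list holder to the sentence in section 6 on who knows the assignment.
- State in both sections whether the 5.1 characteristics are used in allocation. If minimisation is chosen, its predictability to the recruiting doctor needs attention. If they are handled by baseline adjustment instead, 9.2 must change too, since it plans ANOVA for each group and names no covariate-adjusted comparison between groups.

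If a coded list already exists, describe it in these terms.

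The cost is a short amendment to two sections (three with baseline adjustment) and one list, with no extra visits. The downside is that eye numbers may not be exactly 16/16, because the number of patients is not fixed and bilateral patients bring two eyes. The loss of precision is small: 18/14 keeps 98% of the information and 20/12 keeps 94%, treating eyes as independent.

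### When one-eye and two-eye patients are mixed, the plan has no mechanism for reaching its target of 16 eyes per arm

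*Combined protocol and SAP*

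**What the plan says.** - **The size is set in eyes, by arm.** Section 4 foresees "from a minimum of 16 patients to a maximum of 32", "such as to provide the study 32 eyes affected by this condition". Section 5.1 splits these eyes: "In one group of patients with NAION no type of treatment will be performed (16 eyes, Control Group"), and citicoline "for 6 months followed by three months of suspension (16 eyes, Treated Group"). Section 9.1 arrives at 16 eyes per group by raising the PERG requirement of 12 by 30%.
- **Two-eye patients are expected.** Section 5.1 says "it is likely that with the presence of the binocular NAION, both eyes of the patients will be considered as recruited". It adds that 32 patients are needed if all are monocular, and fewer otherwise.
- **Assignment is by patient.** Section 6 says "The assignment to either group will take place in sequential order of presentation of the patient (with a 1:1 probability of being assigned" to either arm), with the aim of two groups equal in number. It does not say whether that number counts patients or eyes. One recruiting doctor decides the group and is the only investigator who knows it.
- **Balancing factors.** Section 5.1 names age, refraction and visual impairment. Having one or two study eyes is not named, although the list is worded as open-ended.
- **Not given.** There is no list, block size, arm-closing rule, or rule for a two-eye patient who would take an arm past 16 eyes. Section 9.2 has no term for laterality.

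**The concern.** The target is counted in eyes and the assignment in patients. The two agree only if every patient contributes the same number of eyes. With a mix, equal patient numbers need not give equal eye numbers, and the plan does not say what happens as one arm approaches 16 eyes.

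Two things are at stake. First, when patient numbers are equal, a gap in eyes is exactly a gap in the number of bilateral patients, so extent of disease becomes tied to arm in a trial of 16 to 32 patients. Second, anyone who tries to hit 16/16 can do so only by choosing where late patients go. The person placed to do that also enrols patients and knows all earlier assignments. Masked assessment does not repair this, because the selection happens before any assessment.

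**Working it through.** **1. The plan's own figure.** Inputs from section 9.1: PERG difference 0.38 microvolts, SDs 0.29 and 0.25, power 90%, alpha 5% (taken as two-sided).
- Pooled SD = √((0.29² + 0.25²)/2) = 0.271, so d = 0.38/0.271 = 1.40.
- A two-sample t-test gives 87.9% power at 11 per arm and 90.7% at 12. The stated 12 is reproduced.
- 12 × 1.30 = 15.6, so 16 is reproduced.

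**2. Exact calculation at 32 eyes.** With b bilateral patients there are 32 − 2b unilateral patients and 32 − b patients in all. Take b = 8: 16 unilateral, 24 patients, bilateral share 8/24 = 33%.

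*Equal patient numbers, 12 per arm.* With j bilateral patients in the treated arm, the arms hold 12 + j and 20 − j eyes, a gap of |2j − 8|. This is also the gap in bilateral patients.
- P(16/16) = C(8,4) × C(16,8) / C(24,12) = 70 × 12,870 / 2,704,156 = 0.333.
- A gap of 4 or more needs j ≤ 2 or j ≥ 6: 2 × (1,820 + 34,944 + 224,224) / 2,704,156 = 0.193. The mildest such case is 6 bilateral patients out of 12 against 2 out of 12.

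*Independent 1:1 draws.* The SD of the eye gap is √(16 × 1² + 8 × 2²) = √48 = 6.93. Exact enumeration gives P(16/16) = 0.113 and P(gap ≥ 4) = 0.669.

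Over b = 1 to 15, P(16/16) is 0.27 to 0.52 with equal patient numbers and 0.10 to 0.14 with independent draws. If all patients are unilateral or all bilateral, equal patient numbers give 16/16 with certainty.

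**3. Simulation.** The documents give neither a bilateral share nor a block size. Assumptions: 20, 33 or 50% of patients bilateral, enrolment stops once 32 eyes are reached, 20,000 trials per setting.

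| Assignment | Gap of 4 or more eyes | Within one eye |
|---|---|---|
| Simple 1:1 by patient | about 63–66% | about 14% |
| Blocks of two patients | about 15–20% | about 37–40% |
| Separate one-eye and two-eye lists, blocks of two | 0% | about 54–59% |

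The zero follows by arithmetic. An unfinished block leaves at most one patient uneven in each list, so the gap is at most 1 + 2 = 3 eyes. At exactly 32 eyes the unilateral count 32 − 2b is even, so the split is 16/16 when b is even and 15/17 when b is odd.

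**4. If an arm were closed at 16 eyes** (no such rule is written), the mean number of patients forced into the other arm would be:

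| Assignment | No bilateral patients | 20–50% bilateral |
|---|---|---|
| Simple 1:1 | 4.5 | about 4.3 down to 3.9 |
| Blocks of two | 1.0 | 1.8–2.0 |

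Laterality therefore adds about one forced patient under blocks of two and none under simple 1:1.

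**5. Power.** With the PERG inputs above, and treating eyes as independent as section 9.1 does, power is 97.0% at 16/16, 96.1% at 12/20 and 94.5% at 10/22.

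**The case against.** A reader might infer that 16 per arm cannot be met. The documents do not support this. Section 5.1 itself foresees an all-monocular trial of 32 patients, where a number-balanced list gives exactly 16/16. With mixed laterality, chance alone achieves it in 27 to 52% of trials when patient numbers are equal.

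A reader might also infer that the plan forces the last patients into one arm. No arm-closing rule is written. Section 9.1 presents 16 as a number considered suitable to reach, already raised from 12, so the plan can be read as enrolling to 32 eyes and accepting near-balance. Most of the forcing that a closed arm would cause comes from having a fixed quota at all, as step 4 shows.

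Three further points are fair:
- The equal-numbers clause in section 6 may have been meant in eyes.
- Under blocks of two, the arms are within two eyes of each other in about 70 to 79% of trials.
- The larger threat is that one doctor decides the group with no concealment described, and that exists with or without bilateral patients.

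All of this limits the point without removing it. Even if section 6 means eyes, it gives no procedure that would balance them.

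**Conclusion.** The concern holds as a gap in the method of assignment. The plan counts its target in eyes, assigns by patient, expects some two-eye patients, and names no step connecting these. Following it with mixed laterality will usually miss 16/16. A gap of four or more eyes arises in about 15 to 20% of trials if patient numbers are kept balanced, and in about 65% if they are not.

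These sizes rest on an assumed bilateral share of 20 to 50% and, for the lower range, assumed blocks of two. They do not apply if laterality is uniform. The cost in power is minor. What matters is comparability of the arms in bilateral disease, and the incentive and opportunity to steer late assignments. This is an improvement that should be made, because it is inexpensive and demonstrably better; it is not a defect that invalidates the design.

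**What to change.** - **Sections 5.1 and 6:** stratify the randomisation by one versus two study eyes, with two pre-generated blocked lists. Someone other than the recruiting doctor should hold them. That doctor registers the patient and the number of study eyes before the assignment is revealed, and no longer decides it. Without concealment, a second list does not prevent steering.
- **Sections 5.1 and 9.1:** state the target as 32 eyes in total, about 16 per arm, so that no arm has to be closed.
- **Section 9.2:** include laterality in the analysis of the outcomes.

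Cost: one extra list, short changes to four sections and one more model term. Final counts may be 15/17 or similar.

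One choice needs care. The recruiting doctor learns past assignments, so the second patient in every block of two is predictable. Longer or varying blocks are harder to guess but allow larger gaps: an unfinished block of four can leave two patients uneven, which is two eyes in the one-eye list and four in the two-eye list. The block scheme should be fixed in advance and kept from that doctor.

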7. TREATMENT OF SUBJECTS

The active form of the food supplement in the study will be manufactured according to Good Manufacturing Principles, GMP and labelled according to the applicable regulatory provisions.

7.1 Dosage, posology and route of administration

During the period of randomized treatment, patients will take the CDP-choline food supplement (Cytidine Diphosphocholine or Citicoline); water; fructose; methylparahydroxybenzoate; potassium sorbate; citric acid. This supplement contains Citicoline in the amount of 500 mg per 10 ml of solution. The supplement is available in this dosage in solution only and is administered in 10 ml vials under the trade name Neukron Oftamese. The treatment dose is 1 vial per day to be taken preferably in the morning for 6 months followed by a period of suspension of 3 months.

7.2 Composition of the treatment in use

The food supplement (Neukron Ofta mese) of the study is produced by Omikron Italia Srl.

Each vial of oral supplement will contain:

10 ml oral solution for use containing:

-CDP-choline (Cytidine Diphosphocholine or Citicoline) 500 mg containing an equivalent of 102 mg of Choline

-Excipients: Osmotised water, Fructose, Potassium sorbate, Citric acid, Methylparahydroxybenzoate

The vials used for the study will be identified by batch number and expiry date.

7.3 Packing of integrator supplement

The samples of Neukron Ofta®mese required for the conducting of the study will be provided free of charge by Omikron Italy.

7.4 Preservation method for integrator supplement

The Investigator must store the samples of food supplement at appropriate temperature and humidity conditions as indicated on the label, in the Institution's internal Pharmacy or in his/her department in a locked room, accessible only to persons authorised to withdraw the samples.

7.5 Drug accountability

The Investigator and the Pharmacy will be responsible for receiving, storing and consigning the food supplement to patients; the Investigator will keep an inventory of the amounts stored and of those returned by individual patients.

7.6 Preservation of materials

The vials of food supplement will be sent to the Pharmacy of the Study Centre and must be stored at the Pharmacy of the Study Centre in a locked area, with access limited to the personnel involved only, out of reach of children, at appropriate temperature and humidity conditions and kept in the boxes provided until used to protect it from exposure to light.

7.7 Concomitant Pharmacological Treatments

Information on concomitant pharmacological treatments includes information on the treatments administered at the time of being included in the study (recorded in the “Ongoing systemic therapies” section of the CRF).

Any pharmacological treatment taken for diseases unrelated to that of the study and considered necessary for the patient's health which does not interfere with the food supplement of the study, may be administered as deemed fit by the Investigator and the GP.

All treatments should be recorded in the CRF, indicating the dosage and date of administration as required.

In addition, if, due to the onset of symptoms and/or signs after commencing administration of the food supplement, the administration of any type of medication should become necessary, this should be reported in the “Ongoing systemic therapies” section of the CRF.

